Official Title:	Sub-Threshold Exercise Treatment for Adolescents with Sport-related Concussion
NCT number:	NCT02710123
Document Type:	Study Protocol and Statistical Analysis Plan
Date of the Document:	10/24/2016

“A Randomized Controlled Trial of Exercise Treatment for Concussion”

Abstract

Background: The University at Buffalo (UB) Concussion Clinic has developed a treadmill test (The Buffalo Concussion Treadmill Test, BCTT) that is the most systematic and only validated approach to the assessment of exercise tolerance in patients with concussion. We have shown that sub-symptom threshold aerobic exercise improves recovery in patients who are slow to recover. The mechanism may involve beneficial effects of exercise on neuroplasticity and upon the abnormal physiology of concussion (autonomic nervous system and control of cerebral blood flow, CBF). We want to evaluate controlled aerobic exercise as a non-pharmacological treatment for concussion during the acute recovery phase in adolescents.

Methods: Subjects (13-18 years old, male and female) who sustained a concussion within the past 4-7 days. We chose this timeframe to make the sample as homogeneous as possible. Subjects will undergo the BCTT on the day of clinic presentation and will then be randomly assigned to daily sub-threshold aerobic or to a progressive stretching program, which is an ideal placebo condition because participants receive equal attention but stretching does not confer a cardiovascular training effect. Polar HR monitors will record their daily activity and HRs and subjects will report symptoms daily on a dedicated website. They will return weekly to see the physician who is blinded to group assignment to determine clinical recovery.

Specific Aim: **To determine the efficacy of early sub-threshold aerobic exercise treatment in adolescents with concussion.** We hypothesize that sub-threshold aerobic exercise as opposed to placebo stretching will safely speed recovery in patients acutely after concussion.

Dependent variable: Time to concussion recovery.

Impact of the project: There is no known active intervention or medication that speeds recovery acutely from concussion. Rest is the most prescribed “treatment”. While a few days of rest are helpful, prolonged rest is actually detrimental to recovery. We are the first group in the world to use the physiological effects of sub-threshold aerobic exercise to safely treat humans with delayed recovery from concussion. There are no data on the use of exercise treatment in the acute phase of concussion recovery although we have completed an RCT that showed it is safe to test exercise tolerance (on the BCTT using our pre-determined stopping criterion) early (within one week) after concussion. The logical next step is to use sub-threshold exercise in those with exercise intolerance shortly after injury to see if it speeds recovery; theoretically because of the beneficial effects of aerobic exercise on autonomic function, CBF control, and neuroplasticity. If successful, this would represent a paradigm shift in the way concussion is assessed and treated. Such an approach may also prevent some of the 20% of adolescents who would have gone on to experience post-concussion syndrome. *We have already enrolled 21 subjects into each group but we need funding to extend this pilot study to satisfy our sample size of 54 in each group in order to obtain an effect size to apply to NIH for a multicenter RCT of early exercise intervention in adolescent concussion. Child and adolescent concussion is an emerging interest area for NIH ([name] was an invited panel member of the recent NIH Pediatric Concussion Workshop held at the NIH on October 13-14, 2016).*

Investigators: PI **[name], MD:** Professor of Clinical Orthopaedics and Rehabilitation Sciences.

[name], PhD: Professor of Psychiatry.

[name], PhD: Professor of Biostatistics

[name], MD: Volunteer faculty – Department of Orthopaedics.

5 Key words: exercise, aerobic, concussion, treatment, physiology

Background/Significance

Concussion is a physiological brain injury that has systemic effects.¹ One of these effects is exercise intolerance, which is defined as inability to exercise to the level predicted for a given age. In previous work we showed that exercise intolerance is an objective sign of ongoing physiological dysfunction after concussion.² Using the principle of exercise intolerance as an objective sign of concussion, we developed a standard treadmill test- the Buffalo Concussion Treadmill Test (BCTT)- that is the only functional test thus far shown to safely³ and reliably⁴ diagnose physiological dysfunction in concussion, help to differentiate it from other conditions with similar subjective symptoms (e.g., cervical and vestibular injury, depression, migraines),⁵ and quantify the clinical severity and exercise capacity of concussed patients.^{3, 4} The BCTT is now used by many others throughout the world to assess concussed patients.

Animal studies have shown that aerobic exercise is beneficial to cognitive recovery if administered three or more weeks after simulated concussion.^{6, 7} Other animal studies show that the motivation for exercise after brain injury is important. Rats forced to exercise 28-32 days and 35-39 days after mild traumatic brain injury (mTBI) markedly stimulated the corticotrophic axis and did not increase brain derived neurotrophic factor (BDNF, which is involved in neuron repair after injury and increases hippocampal volume and improves spatial memory⁸) whereas

BDNF levels increased following *voluntary* exercise.⁹ In another study, rats forced to exercise soon after mTBI increased stress hormone levels whereas rats who voluntarily exercised did not, suggesting that exercise regimens with strong stress responses (i.e., forced exercise) may not be beneficial during the early post-TBI period.¹⁰ Voluntary physical exercise immediately after or within days of TBI has been shown in other animal studies to have beneficial effects on aspects of brain neuroplasticity such as: reduced interhemispheric differences in hippocampal formation and lateral ventricle volumes and in the density of mature neurons in the hilus of the dentate gyrus and the perirhinal cortex,¹¹ increased proliferation of neuronal stem cells,¹² reduced neuronal degeneration and apoptotic cell death around the damaged area,¹³ increased Purkinje neurons and suppressed formation of reactive astrocytes,¹⁴ and better cognitive performance in association with decreased DNA fragmentation in the hippocampus.¹⁵ Similarly, human data suggest that exercise improves brain function via favorable effects on brain neuroplasticity¹⁶ as early as 6 weeks.¹⁷ The rapidity of the beneficial effect of exercise on the brain suggests that the mechanism is not reduced cerebrovascular disease risk but improved neuronal function.

We were the first group to use the animal data to develop an assessment for human patients suffering with prolonged symptoms after concussion (called post-concussion syndrome, PCS). We used the BCTT to establish the symptom-exacerbation exercise threshold and prescribed an individualized, progressive sub-symptom threshold aerobic exercise program for patients with PCS. This controlled exercise program (which is akin to voluntary exercise in animals) safely improved recovery and helped restore function (i.e., return to sport and work) in most patients suffering from PCS.^{3, 5}

[figure not shown]
The results of our early studies led us to query if, in addition to relieving symptoms, exercise might improve the physiology of concussion, which includes abnormal autonomic nervous system (ANS) function and altered control of cerebral blood flow (CBF).¹ In a recent controlled study,¹⁸ we showed that female athletes with PCS had abnormally low sensitivity to the arterial CO₂ tension (PaCO₂) that caused a relative hypoventilation during exercise that raised their PaCO₂ levels out of proportion to exercise intensity. CBF is directly proportional to PaCO₂; hence, elevated PaCO₂ raised exercise CBF disproportionately to exercise intensity. This was associated with symptoms of headache and dizziness that limited their exercise tolerance to low levels. A program of sub-threshold aerobic exercise treatment increased their CO₂ sensitivity to normal, which normalized exercise ventilation, PaCO₂ levels, and exercise tolerance. Thus, sub-threshold aerobic exercise had salutary effects not only on the symptoms but on the physiology of the concussed brain in active patients suffering with PCS. In a different study we showed that sub-threshold aerobic exercise treatment restored abnormal local CBF regulation (as indicated by brain functional MRI, fMRI, activation patterns) to normal in PCS patients whereas a placebo stretching program did not.¹⁹ Thus, these studies suggest that concussion symptoms and exercise intolerance may be related to abnormal CBF regulation and, furthermore, that individualized, controlled aerobic exercise treatment can restore CBF regulation and exercise tolerance to normal and improve outcome.

The traditional therapy for concussion and for PCS has been rest and avoidance of activity that exacerbates symptoms.²⁰ Physical deconditioning from prolonged rest can, however, impair control of CBF²¹ whereas exercise training improves CBF control²² as well as ANS balance.² The ability to exercise to exhaustion on a treadmill test without symptom exacerbation defines physiological recovery from concussion,¹⁹ which conforms to expert consensus opinion about

recovery from concussion and readiness to return to activity.²⁰ Individualized exercise treatment for PCS patients is well accepted as < 10% of subjects refuse exercise treatment.⁵ We have recently completed an RCT (paper in review) of giving the BCTT to concussed adolescents within 4 days from injury (range 1-9 d) and showed that it was completely safe (Figure) without short term increase in symptoms or delayed recovery when compared with standard assessment (i.e., no exercise testing).

While adults typically recover within 10-14 days after concussion,²⁰ adolescents may take 3-4 weeks to recover.^{23,24} Since we have shown that it is safe to assess exercise capacity shortly after concussion (Figure), the use of sub-threshold aerobic exercise as a non-pharmacological treatment to speed recovery acutely after concussion in adolescents should be tested in a randomized controlled trial (RCT).

Methods: Patients will be screened for eligibility at the UB Concussion Management Clinics in Buffalo and in Niagara Falls. Potential subjects will be identified after a standard clinical evaluation that consists of a thorough history and physical examination by physicians with extensive experience in concussion management. Concussion will be diagnosed according to international consensus definition.²⁰

Inclusion Criteria: Age 13-18 years; any race, ethnicity, or sex; concussion within 4-7 days of first clinic visit; symptom score >5 on the Post-Concussion Scale;²⁵ low risk for cardiac disease (defined as no cardiopulmonary symptoms and meet no more than one risk factor for heart disease);²⁶ submaximal symptom-limited threshold on the BCTT;²⁷ willing to exercise; and medications, except for β-blockers, are acceptable.

Our symptom-limited graded exercise test (BCTT) is terminated when concussed subjects have an increase of ≥ 3 points on the VAS. We have shown that performing the BCTT within one week of concussion does

Exclusion Criteria: Glasgow Coma Scale (GCS) score <12 at time of injury. Justification: indicates moderate or severe TBI; Lesion on CT/MRI (via review of emergency room medical records) and/or focal neurologic deficit. Justification: indicates moderate or severe TBI; Inability to exercise because of orthopedic injury, significant vestibular dysfunction, visual abnormality, or increased cardiac risk. Justification: unsafe to perform treadmill test or undergo exercise as treatment; β-blocker use. Justification: affects autonomic function, reduces exercise capacity, and blunts exercise heart rate, invalidating interpretation of the treadmill test; Major depression. Justification: affects autonomic function, unlikely to comply with intervention; Unwilling to exercise. Justification: will not be compliant with intervention or control condition; and cannot understand English. Justification: cannot be compliant with intervention.

Specific Aim: To determine the efficacy of early sub-threshold aerobic exercise treatment in patients with concussion. We hypothesize that sub-threshold aerobic exercise as opposed to placebo stretching will safely speed recovery in patients acutely after concussion.

Approach (we already have IRB approval)

If eligible, subjects will meet immediately with the research assistant to obtain consent. Subjects will fill out a validated concussion symptom checklist that has normative data.²⁵ Subjects will be treadmill tested for exercise tolerance on day of enrollment (or the next day if too symptomatic, which we define as a score of ≥ 7 on our 1-10 VAS) using our pre-determined stopping criterion (symptom exacerbation).²⁷ Subjects will be randomly assigned to sub-threshold aerobic exercise or to placebo (low level stretching that does not raise HR) therapy.

Subjects will be given a Polar HR monitor that records daily activity (via accelerometer) and HR (via chest strap) and asked to wear it at all times at home but for shower and swimming. Subjects randomized to aerobic exercise will exercise at a target HR intensity (80% of the HR achieved on the treadmill) 20 minutes per day (on a stationary bike or treadmill under supervision of parent/partner, at home or in a gym). They will be instructed to stop exercise at symptom exacerbation or at 20 min, whichever comes first. We have shown that this is safe.³ They will be prompted by text/email to do their exercise at the same time each day. Subjects randomized to placebo will be contacted by text/email each day to prompt them to stretch for 20 minutes per day (stretching program provided via written instructions with visual examples of each stretch).¹⁹ Subjects will complete an activity log to document exercise times. We used a similar intervention in a small controlled trial of exercise vs. placebo stretching in PCS patients and showed that aerobic exercise improved symptoms and returned brain fMRI activation patterns to control levels whereas placebo stretching did not.¹⁹ After randomization, subjects will be seen weekly by a physician blinded to treatment group until they are declared recovered (by normal symptoms and physical examination). They also will have treadmill testing and have accelerometer/HR data downloaded weekly for up to 3 weeks (Visits 3-5). A new exercise prescription will be given to subjects based upon the treadmill results (a new target HR or a new stretching prescription). Concussion care provided by the blinded physician will be otherwise the same for each group.

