We used data from a pilot study of exercise versus stretching in concussed patients³⁰ and estimated 4.2 and 7.8 as the standard deviation of the days to recovery for the aerobic exercise and stretching exercise groups, respectively. We used an underlying normal distribution to simulate time to recovery data with the above standard deviations. Using a two sample two-sided t-test, we calculated an 80 percent chance to detect a clinically significant mean difference of 3.7 days in recovery time between groups with 50 participants in each group. No interim analysis was planned. Adverse events and near misses were recorded and evaluated by the treating physician.

Data Analysis

Analyses were based on per protocol analysis. Baseline characteristics were analyzed to assess cluster differences between aerobic and stretching groups. We assessed group-wise differences in normally distributed variables (age, total physical examination findings, total symptom severity scores on initial visit, and days to initial visit) using ANOVA. Chi-square test was used to assess group-wise differences in sex and prior concussions. The Mann-Whitney test was used for the main outcome measure (days to recovery), which was not normally distributed. This outcome was demonstrated by Kaplan-Meier curves and assessed using multivariable Cox proportional hazards models, which were adjusted for patient characteristics (age, sex, prior concussion, and time since injury) based on prior literature.³⁴ The Mann-Whitney test was also used for the analysis of days to recovery from first clinical visit. Mean daily symptom severity score with 95% CI for the first three weeks was considered in linear regression models and distributional checks of residuals were undertaken to determine the most appropriate model. Missing values were calculated as the average of day-before and day-after scores. A repeated

measures ANOVA was used to assess differences in symptom recovery time between groups.

A p-value less than 0.05 determined statistical significance and all tests were 2-sided. Statistical analyses were performed using STATA version 14 (College Station, Texas).

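### The entry treadmill threshold is known for every participant before randomisation, but the adjusted Cox model omits it and contains no baseline severity measure

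*Combined protocol and SAP*

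**What the plan says.** **Availability.** The Inclusion Criteria require a "submaximal symptom-limited threshold on the BCTT", so every eligible participant has a value. The Abstract gives the order: "Subjects will undergo the BCTT on the day of clinic presentation and will then be randomly assigned". The Approach section describes the same sequence, allowing the test on the next day for those who are too symptomatic.

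**Meaning.** Background/Significance says the BCTT can "quantify the clinical severity and exercise capacity of concussed patients".

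**Use.** Apart from eligibility, the entry result has one stated use. It sets the aerobic target, at "80% of the HR achieved on the treadmill".

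**Analysis.** Under Data Analysis, days to recovery is compared with a Mann-Whitney test, which has no covariates. The Cox models are "adjusted for patient characteristics (age, sex, prior concussion, and time since injury"). The baseline comparisons listed there include symptom severity and examination findings, but not the treadmill threshold, and none of these three enters the Cox model. The shorter Statistical Analysis paragraph in the protocol refers to regression and names no covariates.

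**Clinic.** Screening takes place at the "UB Concussion Management Clinics in Buffalo and in Niagara Falls". The Approach section says "Subjects will be randomly assigned to sub-threshold aerobic exercise or to placebo" and describes no method or stratification factor. Participants are then "seen weekly by a physician blinded to treatment group until they are declared recovered".

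**The concern.** A baseline variable that predicts the outcome and is on file for everyone is normally worth including in an adjusted analysis. In a linear model it removes outcome variance. In a Cox model it mainly moves the estimated hazard ratio away from 1. In either case it corrects for chance imbalance between arms on that variable.

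The four listed covariates describe who the patient is and when the injury happened. None says how badly affected the patient was at entry. The threshold is the measure that the protocol itself puts forward for that, and the trial both selects on it and prescribes from it.

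What is at stake is precision in a trial of about 50 per arm whose protocol seeks an effect size for planning a larger study. The validity of the comparison is not at stake.

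**Working it through.** **Inputs from the Sample Size section.** SDs of days to recovery are 4.2 (aerobic) and 7.8 (stretching); difference 3.7 days; 50 per arm; two-sided t-test; stated power 80%. Data Analysis sets the 0.05 level.

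**Assumed input.** The correlation r between entry threshold and days to recovery within arm. The documents give none, so I use 0.2 to 0.4 as a range.

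**Step 1: the plan's own figure.**
- Mean within-arm variance = (4.2² + 7.8²)/2 = (17.64 + 60.84)/2 = 39.24, so SD = 6.264 days.
- Standard error of the difference = √(17.64/50 + 60.84/50) = 1.253.
- Noncentrality = 3.7/1.253 = 2.953; critical t on 98 df = 1.984.
- Power = 83.3% (pooled noncentral t), 83.0% (Welch) or 84.0% (normal approximation).

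The stated 80% is not reproduced by the t-test. Simulating the Mann-Whitney test on the same normal data gives 80.5%. The gap is on the conservative side and does not affect this point; 83.3% is the base below.

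**Step 2: adding the threshold to a linear model on days.** The residual SD is multiplied by √(1 − r²). The equivalent gain in sample size per arm is 50/(1 − r²) − 50.

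| r | variance removed (r²) | residual SD | noncentrality | power | equivalent extra per arm |
|---|---|---|---|---|---|
| 0 | 0% | 6.264 | 2.953 | 83.3% | 0 |
| 0.2 | 4% | 6.138 | 3.014 | 84.7% | 2.1 |
| 0.3 | 9% | 5.976 | 3.096 | 86.6% | 4.9 |
| 0.4 | 16% | 5.741 | 3.222 | 89.1% | 9.5 |

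The gain is 84.7 − 83.3 = 1.4 points to 89.1 − 83.3 = 5.8 points. Losing one degree of freedom (97 instead of 98) when r = 0 leaves power at 83.3% to one decimal.

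**Step 3: the same effect seen as chance imbalance.** With no adjustment, imbalance in the threshold moves the arm difference with SD r × 6.264 × √(2/50) = r × 1.253. That is 0.25 days at r = 0.2 and 0.50 days at r = 0.4, or 7% and 14% of the 3.7-day target. This restates Step 2 and is not an additional loss.

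**Step 4: does it carry over to the Cox model?** Only in direction. In simulations of 400 runs under the plan's normal assumptions, Cox power at 3.7 days was near 99% with or without the covariate, so there was no room to see a gain. At a 2-day difference with r = 0.4 it was about 83% without and 86% with. Each of those has a simulation standard error of about √(0.85 × 0.15/400) = 1.8 points, so the 3-point gap shows direction at most.

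**The case against.** **The size is assumed throughout.** This stands. Calling a test a severity measure is not evidence of how well it predicts days to recovery, and requiring a submaximal threshold at entry may narrow its range and weaken any correlation. The four planned covariates may also absorb part of the gain.

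**The covariates were chosen from prior literature.** Data Analysis says so, and the documents do not show whether the threshold was considered there. A list can always be lengthened with recorded variables. This has force against covariates in general, but less against the only objective severity measure that the protocol itself promotes, when the list has none.

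**The main test would not change.** Correct. Adding the threshold to the Cox model leaves the Mann-Whitney comparison unadjusted for it.

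**The change may be post hoc.** Data Analysis is written in the past tense and reports that the outcome was not normally distributed. If outcome data had been seen, a new covariate is no longer a free prespecified term.

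**The threshold also sets the exercise dose.** This is not a reason to leave it out. The entry value is measured before assignment in both arms, so adjusting for it does not remove treatment effect.

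**Stronger readings to avoid.** A reader might infer that differences between the two clinics leave removable noise in a physician-judged outcome. The documents say only that patients are screened at two clinics. They do not say where follow-up takes place, whether assessors differ by clinic, or how participants split. A reader might also infer that randomisation was unstratified; the text describes no stratification, which is silence and not a statement. Nor does the omission bias the comparison.

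**Conclusion.** The point holds as a low-priority improvement. The entry BCTT threshold exists for every participant before randomisation and is presented by the protocol as a severity measure, and the Cox model has no baseline severity term.

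The consequence is a possible loss of efficiency. On the assumption that r is 0.2 to 0.4, and for a linear model on days with the plan's SDs, it is worth about 1 to 6 points of power, or about 2 to 10 participants per arm. For the Cox model the size is not established and may be smaller. If the threshold does not predict recovery, nothing is gained and almost nothing is lost. The documents do not support a claim that a meaningful amount of noise is being left in, and they support no figure for clinic.

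**What to change.** In Data Analysis, add the entry BCTT threshold to the Cox model as a continuous covariate alongside the four already listed, defined as heart rate at symptom-limited stopping on the pre-randomisation test. The cost is one sentence in the SAP and about one degree of freedom; no new data, visits or participants are needed.

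State when the covariate list was fixed. If any outcome data had been seen by then, keep the four-covariate model as written and report the model with the threshold as a labelled sensitivity analysis.

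Optional and minor: state where follow-up and recovery assessment took place. If both clinics were used, stratify the Cox model by clinic, with a separate baseline hazard for each.
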